11. MEASUREMENT OF EFFECT

11.1 Antitumor Effect – Solid Tumors

For the purposes of this study, participants should be re-evaluated for response every 8 weeks. In addition to a baseline scan, confirmatory scans should also be obtained 8 weeks following initial documentation of objective response.

Response and progression will be evaluated in this study using the new international criteria proposed by the Response Evaluation Criteria in Solid Tumors (RECIST) guideline (version 1.1) [Eur J Ca 45:228-247, 2009]. Changes in the largest diameter (unidimensional measurement) of the tumor lesions and the shortest diameter in the case of malignant lymph nodes are used in the RECIST criteria.

11.1.1 **Definitions**

Evaluable for Target Disease response. Only those participants who have measurable disease present at baseline, have received at least one cycle of therapy, and have had their disease re-evaluated will be considered evaluable for target disease response. These participants will have their response classified according to the definitions stated below. (Note: Participants who exhibit objective disease progression prior to the end of cycle 1 will also be considered evaluable.)

Evaluable Non-Target Disease Response. Participants who have lesions present at baseline that are evaluable but do not meet the definitions of measurable disease, have received at least one cycle of therapy, and have had their disease re-evaluated will be considered evaluable for non-target disease. The response assessment is based on the presence, absence, or unequivocal progression of the lesions.

11.1.2 **Disease Parameters**

Measurable disease. Measurable lesions are defined as those that can be accurately measured in at least one dimension (longest diameter to be recorded) as 2: 20 mm by chest x-ray or 2:10 mm with CT scan, MRI, or calipers by clinical exam. All tumor measurements must be recorded in millimeters (or decimal fractions of centimeters).

Note: Tumor lesions that are situated in a previously irradiated area might or might not be considered measurable.

Malignant lymph nodes. To be considered pathologically enlarged and measurable, a lymph node must be 2:15 mm in short axis when assessed by CT scan (CT scan slice thickness recommended to be no greater than 5 mm). At baseline and in follow-up, only the short axis will be measured and followed.

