11.1.4.3 Evaluation of New Lesions

The finding of a new lesion should be unequivocal (i.e. not due to difference in scanning technique, imaging modality, or findings thought to represent something other than tumor (for example, some 'new' bone lesions may be simply healing or flare of pre-existing lesions). However, a lesion identified on a follow-up scan in an anatomical location that was not scanned at baseline is considered new and will indicate PD. If a new lesion is equivocal (because of small size etc.), follow-up evaluation will clarify if it truly represents new disease and if PD is confirmed, progression should be declared using the date of the initial scan on which the lesion was discovered.

11.1.4.4 **Evaluation of Best Overall Response**

The best overall response is the best response recorded from the start of the treatment until disease progression/recurrence (taking as reference for progressive disease the smallest measurements recorded since the treatment started). The patient's best response assignment will depend on the achievement of both measurement and confirmation criteria.

For Participants with Measurable Disease (i.e., Target Disease)

Target Lesions	Non-Target Lesions	New Lesions*	Overall Response	Best Overall Response when Confirmation is Required*
CR	CR	No	CR	>4 wks Confirmation**
CR	Non-CR/Non- PD	No	PR	
CR	Not evaluated	No	PR	→4 wks Confirmation**
PR	Non-CR/Non- PD/not evaluated	No	PR	
SD	Non-CR/Non- PD/not evaluated	No	SD	Documented at least once ≥4 wks from baseline**
PD	Any	Yes or No	PD	
Any	PD***	Yes or No	PD	no prior SD, PR or CR
Any	Any	Yes	PD	

^{*} See RECIST 1.1 manuscript for further details on what is evidence of a new lesion.

Note: Participants with a global deterioration of health status requiring discontinuation of treatment without objective evidence of disease progression at that time should be reported as "symptomatic deterioration." Every effort should be made to document the objective progression even after discontinuation of treatment.

For Participants with Non-Measurable Disease (i.e., Non-Target Disease)

|--|

^{**} Only for non-randomized trials with response as primary endpoint.

^{***} In exceptional circumstances, unequivocal progression in non-target lesions may be accepted as disease progression.

CR	No	CR
Non-CR/non-PD	No	Non-CR/non-PD*
Not all evaluated	No	not evaluated
Unequivocal PD	Yes or No	PD
Any	Yes	PD

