A two-stage Simon optimal design was used where if ≥ 7 patients were alive and disease was progression-free at 10 months among 21 evaluable (eligible and began protocol treatment) patients (assuming that ≥ 2 patients among 8 evaluable patients accrued in the first stage were alive and disease progression-free at 10 months), further testing of this regimen was to be considered. The probability of concluding the regimen was effective was 81% if the true proportion progression-free was 42%. The probability of concluding the regimen as effective was 10% if the true proportion progression-free was 20%. Allowing 2 patients to not begin protocol treatment or to be classified as ineligible, a total of 23 patients with MTC were to be entered.

Rationale for Patient Population and Design Changes (2019).

A total of 8 patients with MTC have been enrolled. Due to the changing treatment landscape/other treatment options for patients with MTC, the trial will no longer enroll patients with MTC. Patients with DTC will now be enrolled in order to obtain preliminary information on efficacy using regorafenib in this patient population.

Revised Endpoint and Statistical Design for patients with DTC

With only 2 treatment options currently FDA approved for RAIR DTC and their corresponding response rates, the study chair felt that an overall response rate >25% by using regorafenib would be worth further study. The below design and specific operating characteristics were chosen to rule out a best overall response rate of 25% by studying approximately n=22 patients with DTC. Therefore ,keeping within the original overall accrual goal from when the trial opened (approximately 31 (n=8 MTC plus n=22 DTC)) and that only large improvements in response will be able to be detected statistically.

A two-stage Simon optimal design will be used to stop the trial early if there is minimal activity in this patient population. In the first stage, accrual will continue until 9 evaluable patients (eligible and begin protocol treatment) with DTC are entered. If there are \leq 2 patients with disease in response, accrual to the trial will be closed with the conclusion that there is little evidence that the response rate would reach 49%. The probability that the trial will close early is 60% if the true response rate is 25%.

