If there are ≥ 3 patients with disease in response among 9 evaluable patients, the trial will continue to accrue patients until a total of 20 evaluable patients are entered. If there are ≥ 8 patients w i t h d i s e a s e i n r es p o n s e a m o n g 2 0 evaluable patients, further testing of this regimen will be considered. The probability of concluding the regimen as effective is 81% if the true response rate is 49%. The probability of concluding the regimen as effective is 9% if the true r e s p o n s e r a t e i s 2 5%. Allowing 2 patients to not begin protocol treatment or be classified as ineligible, a total of 22 patients could be entered.

The primary efficacy population includes all eligible patients who begin protocol treatment. The proportion progression-free at 10 months for patients with MTC and the response rate for patients with DTC will be summarized as a proportion with a corresponding exact 95% binomial confidence interval. Safety will be assessed via the CTCAE and frequencies of adverse events will be summarized. Time-to-event endpoints will be estimated using the Kaplan-Meier method and 95% confidence intervals for the median or time-specific event time will be summarized. Another endpoint is to assess quality of life (QOL). QOL will be assessed via self-report questionnaires at the timepoints outlined in the Study Calendar. Descriptive statistics from the responses from the questionnaires will be summarized across timepoints of assessment. Rates of drop-out/non-response to QOL assessments and corresponding reason will also be summarized across timepoints of assessment.

With an estimated monthly accrual of 1 - 2 patients with DTC, the first stage is estimated to complete accrual in approximately 6-8 months. As is customary with this type of design, accrual will be suspended after the first stage (n=9 evaluable patients) in order to assess outcome, however, this suspension is also dependent on the actual observed accrual rate and the number of patients' disease confirmed in CR or PR while the first stage of the trial is accruing.

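### Do two meanings of 'evaluable' leave the primary DTC response rate and its type I error open to inflation?

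*Combined protocol and SAP*

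**What the plan says.** Section 13.1 sets the DTC decision rule. In the first stage "accrual will continue until 9 evaluable patients (eligible and begin protocol treatment) with DTC are entered"; two or fewer responders close the trial. With three or more "patients with disease in response among 9 evaluable patients, the trial will continue to accrue patients until a total of 20 evaluable patients are entered", and at least 8 responders among those 20 support further testing. The stated properties are 9% type I error at a true rate of 25%, 81% power at 49%, and a 60% chance of early closure at 25%. Two extra entries, 22 in all, cover patients who never start treatment or prove ineligible. The paragraph that specifies the response-rate estimate and its exact interval opens with "The primary efficacy population includes all eligible patients who begin protocol treatment".

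Section 11.1.1, within the RECIST measurement rules, defines a different set for target-disease response: patients with measurable disease who "have received at least one cycle of therapy, and have had their disease re-evaluated will be considered evaluable for target disease response". A note keeps in those with objective progression before the end of cycle 1.

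On confirmation, Section 11.1 says "confirmatory scans should also be obtained 8 weeks following initial documentation of objective response". The best-response table in Section 11.1.4.4 shows confirmation at more than 4 weeks, with the footnote "Only for non-randomized trials with response as primary endpoint", which describes this trial.

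**The concern.** One word carries two definitions, and the primary DTC endpoint depends on it. A patient who stops in cycle 1 for toxicity, withdrawal or clinical decline belongs to the Section 13.1 denominator, but receives no response category under Section 11.1.1. No sentence says which definition prevails or that such a patient counts as a non-responder.

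If the Section 11.1.1 set were used for the primary rate, the patients removed would nearly all be non-responders, so the estimate would be biased upward. If they were also replaced, both the 3-of-9 gate and the 8-of-20 rule would be easier to pass with an inactive drug. The escalating dose schedule was adopted for tolerability, so early exits are not far-fetched, and one patient separates 7 from 8 responders. The 8-week and 4-week confirmation figures look like a second inconsistency, this time in the numerator.

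**Working it through.** **Inputs.** From Section 13.1: null rate 25%, target rate 49%, continue with at least 3 of 9, succeed with at least 8 of 20, 22 entries. From Section 1.1: up to 24 DTC patients. The share *d* of treated patients whom Section 11.1.1 would drop is not in the documents. It is assumed to be 5% to 20%, all non-responders.

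**1. The plan's own figures.** Early closure at 25% = P(Bin(9, 0.25) ≤ 2) = 0.0751 + 0.2253 + 0.3003 = 0.6007 (stated 60%).

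Type I error = Σ over x = 3 to 9 of P(Bin(9, 0.25) = x) × P(Bin(11, 0.25) ≥ 8 − x). The terms for x = 3 to 8 are 0.0268 + 0.0335 + 0.0212 + 0.0069 + 0.0012 + 0.0001 = 0.0897; x = 9 adds nothing at this precision (stated 9%). The same sum at 49% gives 0.8062 (stated 81%). All three reproduce with all eligible treated patients in the denominator.

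**2. If the Section 11.1.1 set were used for the stage counts instead.** The null rate among the patients kept becomes 0.25/(1 − d). Reaching 20 of them takes 20/(1 − d) treated patients on average. The success rule stays at 8 or more responders.

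| Assumed loss d | Null rate among those kept | Mean treated to reach 20 | Type I error: unlimited replacement | Capped at 24 treated | Capped at 22 treated | No replacement (20 treated) |
|---|---|---|---|---|---|---|
| 5% | 26.3% | 21.1 | 11.5% | 11.4% | 11.2% | 9.2% |
| 10% | 27.8% | 22.2 | 14.6% | 14.3% | 12.9% | 9.5% |
| 15% | 29.4% | 23.5 | 18.7% | 17.1% | 14.1% | 9.7% |
| 20% | 31.3% | 25.0 | 24.0% | 19.3% | 14.9% | 9.8% |

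With unlimited replacement, early closure under the null falls from 60% to 52% at 10% loss and 43% at 20%.

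The last column rises slightly only because the interim look waits for nine re-evaluated patients, so a few more have been treated by then. It has a ceiling. Success needs 8 responders among 20 treated patients, and P(Bin(20, 0.25) ≥ 8) = 0.102 whatever the interim look does.

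**3. The estimate.** Seven responders are 7/20 = 35.0% of treated patients and 7/17 = 41.2% if three are dropped. The decision is the same in both cases, since 7 is below 8. A rule of 40% or more of re-evaluated patients, which would give a type I error of roughly 9% to 18% over the same losses, appears nowhere in the plan.

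**4. Confirmation.** More than 4 weeks is a minimum. Imaging is 8-weekly (Section 10, note c), and a confirmatory scan 8 weeks after first response satisfies that minimum. Section 11.1.4.4 makes best response depend on confirmation as well as measurement.

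**The case for a change.** The best case for a change is that Section 11 is where RECIST response is defined, the primary DTC objective is response by RECIST, and Section 11.1.1 says that only its own set is evaluable. The safeguards are partial. The end-of-treatment scan (Section 10, note e) helps a patient who finishes cycle 1 and stops before week 8, but not one who stops during cycle 1. The exception for early progression covers objective progression only, while Section 5.8 also takes patients off treatment for clinical progression, adverse events and withdrawal. In the colorectal dosing trial cited in Section 2.3.2, 43% of patients on the escalating schedule entered cycle 3, about when the first scan falls here. That figure may include progressors and comes from another disease, so it gives no loss rate for DTC, but early exits are plausible.

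This establishes that the wording is loose and lacks a cross-reference. It does not establish that the primary analysis is ambiguous. Section 11.1.1 describes whose target-lesion response gets classified; it does not claim to set the analysis population or the stage counts. Section 13.1 does both, explicitly. Once the denominator is all eligible treated patients, anyone without a recorded CR or PR is in the denominator and not in the numerator, which is to count as a non-responder. The spare entries are for untreated or ineligible patients only, so they give no licence to replace someone treated.

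**Conclusion.** No change is needed. The specific definition in Section 13.1 governs the primary DTC response rate and both stage decisions. Followed as written, it delivers the stated properties (8.97%, 80.6% and 60.1% on recalculation). The figures of 11.5% to 24.0% describe a trial that uses the Section 11.1.1 set for the stage counts and replaces early leavers without limit. The plan provides for neither step, and at 20% loss the average of 25 treated patients exceeds both the 22 in Section 13.1 and the 24 in Section 1.1. Using the wrong set without replacement would leave type I error below 10% at losses up to 20%. The remaining exposure is a reported percentage on the wrong denominator, and Section 13.1 already names the right one. The confirmation intervals are compatible.

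The sizes given for misuse rest on assumed losses of 5% to 20%, with every lost patient a non-responder. The conclusion does not depend on those assumptions, because the planned analysis loses no treated, eligible patient. What is left is a missing cross-reference that an analyst resolves by following Section 13.1, with no effect on any planned result.

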11.1.3 Methods for Evaluation of Disease

All measurements should be taken and recorded in metric notation using a ruler, calipers, or a digital measurement tool. All baseline evaluations should be performed as closely as possible to the beginning of treatment and never more than 4 weeks before the beginning of the treatment.

The same method of assessment and the same technique should be used to characterize each identified and reported lesion at baseline and during follow-up. Imaging-based evaluation is preferred to evaluation by clinical examination unless the lesion(s) being followed cannot be imaged but are assessable by clinical exam.

Clinical lesions. Clinical lesions will only be considered measurable when they are superficial (*e.g.*, skin nodules and palpable lymph nodes) and 2:10 mm in diameter as assessed using calipers (*e.g.*, skin nodules). In the case of skin lesions, documentation by color photography, including a ruler to estimate the size of the lesion, is recommended.

Chest x-ray. Lesions on chest x-ray are acceptable as measurable lesions when they are clearly defined and surrounded by aerated lung; however, CT is preferable.

Conventional CT and MRI. This guideline has defined measurability of lesions on CT scan based on the assumption that CT thickness is 5mm or less. If CT scans have slice thickness greater than 5 mm, the minimum size of a measurable lesion should be twice the slice thickness. MRI is also acceptable in certain situations (*e.g.* for body scans).

Use of MRI remains a complex issue. MRI has excellent contrast, spatial, and temporal resolution; however, there are many image acquisition variables involved in MRI, which greatly impact image quality, lesion conspicuity, and measurement. Furthermore, the availability of MRI is variable globally. As with CT, if an MRI is performed, the technical specifications of the scanning sequences used should be optimized for the evaluation of the type and site of disease. Furthermore, as with CT, the modality used at follow-up should be the same as was used at baseline and the lesions should be measured/assessed on the same pulse sequence. It is beyond the scope of the RECIST guidelines to prescribe specific MRI pulse sequence parameters for all scanners, body parts, and diseases. Ideally, the same type of scanner should be used and the image acquisition protocol should be followed as closely as possible to prior scans. Body scans should be performed with breath-hold scanning techniques, if possible.

FDG-PET/CT Imaging.

Patient Preparation

Patients should avoid any strenuous exercise for 24 hours prior to the PET scan and fast for no less than 4 hours prior to the injection of FDG. Patients must have a fasting blood glucose level :S 200 mg/dL prior to FDG injection. An attempt should be initially made to control the blood glucose level, which will require the rescheduling of the injection. If the glucose level cannot be controlled (i.e. > 200 mg/dL), the patient will not be included in the FDG-PET/CT imaging. Patients should be adequately hydrated with plain water. Weight (kg), height (cm), and blood glucose (mg/dL) will be measured and recorded prior to the injection of FDG. Sedation (alprazolam, 0.5-1 mg, po, 30 minutes pre-FDG injection) is allowed, but not mandatory and should be used consistently by the patient for all scans. Filgrastim, pegfilgrastim, and epoetin are known to affect FDG uptake, and their use by the patient should be recorded. Patients should wait in a warm room to avoid false positive brown fat FDG uptake. Patients will lie supine in a quiet room during the FDG uptake period. FDG will be synthesized and prepared in accordance with the institution's standard procedures or obtained from a commercial supplier.

FDG Dosing and Administration

The administered activity of FDG should be based on the PET/CT system manufacturer's recommendation. The recommended FDG dose is 0.14-0.21 mCi/kg. The actual FDG dose should be a bolus of 8-20 mCi, followed by a saline flush (per institutional procedure). Preinjection FDG Syringe dose, FDG dose injected and Post-injection FDG dose residual and corresponding time should be documented.

FDG-PET/CT Imaging Acquisition

Whole body PET/CT acquisition at both pre-therapy (baseline) and on follow ups MUST start 70 (\pm 10) minutes after FDG injection. The timing should stay the same for follow- up PET/CT scans from the baseline (no more than a \pm 10 minute difference). It is critical that follow-up PET/CT scans will be performed in an identical way to the baseline scan, with the same scanner, same scan direction (skull to thighs or thighs to skull), and consistent arm positioning (arms up or arms down). Preferably, schedule the patient for both baseline and follow-up scans at the same time of day (AM or PM) to

improve reproducibility. The field of view is to encompass the region between the scalp and toes. Patient will be scanned supine with arms positioned comfortably above the head, if possible. Oral and/or IV contrast is optional. Patient should empty his/her bladder immediately before the acquisition of images. For the emission scanning, the acquisition should be performed in 2D or 3D mode in accordance with the manufacturer's recommendations. The emission scan must be corrected for scatter, random events, and dead-time losses using the manufacturer's recommended procedure. The image reconstruction will be performed using the manufacturer recommended parameters. Images should be attenuation corrected using CT data (note that if IV contrast is used, blood FDG SUV may be altered; therefore attenuation correction must be done without contrast).

11.1.4 **Response Criteria**

11.1.4.1 Evaluation of Target Lesions

Complete Response (CR): Disappearance of all target lesions. Any pathological lymph nodes (whether target or non-target) must have reduction in short axis to <10 mm.

Partial Response (PR): At least a 30% decrease in the sum of the diameters of target lesions, taking as reference the baseline sum diameters.

Progressive Disease (PD): At least a 20% increase in the sum of the diameters of target lesions, taking as reference the smallest sum on study (this includes the baseline sum if that is the smallest on study). In addition to the relative increase of 20%, the sum must also demonstrate an absolute increase of at least 5 mm. (Note: the appearance of one or more new lesions is also considered progressions).

Stable Disease (SD): Neither sufficient shrinkage to qualify for PR nor sufficient increase to qualify for PD, taking as reference the smallest sum diameters while on study.

11.1.4.2 **Evaluation of Non-Target Lesions**

Complete Response (CR): Disappearance of all non-target lesions and normalization of tumor marker level. All lymph nodes must be non-pathological in size (<10 mm short axis).

Note: If tumor markers are initially above the upper normal limit, they must normalize for a patient to be considered in complete clinical response.

Non-CR/Non-PD: Persistence of one or more non-target lesion(s) and/or maintenance of tumor marker level above the normal limits.

Progressive Disease (PD): Appearance of one or more new lesions and/or *unequivocal progression* of existing non-target lesions. *Unequivocal progression* should not normally trump target lesion status. It must be representative of overall disease status change, not a single lesion increase.

Although a clear progression of "non-target" lesions only is exceptional, the opinion of the treating physician should prevail in such circumstances, and the progression status should be confirmed at a later time by the review panel (or Principal Investigator).

